### 4.5. Monitoring Plan

Monitoring will be performed by a trained person appointed by Philips to ensure compliance with the clinical study plan, applicable national regulations and international standards, patient safety and data validity. The Sponsor may designate one or more individuals to monitor the progress of a clinical study. The Sponsor may also delegate the monitoring responsibilities to a third party. However, the Sponsor remains ultimately responsible for the conduct of the study. The Institution is responsible for the appropriate de-identification of subject data. The investigational site should provide access to the source data of the subjects.

The first visit will occur as soon as possible after the first subject is enrolled at each study site. The monitoring schedule is based on the following considerations: enrollment rate, study compliance at the center, magnitude of data corrections required, study stage (e.g. start-up or follow-up), complexity of the study, IRB/MEC request, audit/inspection.

The monitor activities include:

- Check that the study is conducted, recorded and reported in compliance with this clinical study plan, and applicable regulations. Acts to oversee the progress of the study.
- Check signed and dated informed consent of the subjects and check that this is signed before any study-related procedures are undertaken.

Philips IGT Systems Status: Final	Post-Market Clinical Study Plan Contrast volume reduction during PCI with the use of Dynamic Coronary Roadmap	XY607-130198 2017 Aug 15 Revision: 1.0 Page 11 of 16
---	---	---

- Ensure that essential documents (e.g.contract, MEC approval) are maintained in the Investigator Site File.
- Ensure recording of deviations from protocol and store in Investigator Site File or CRF.
- Ensure that the principal investigator is informed and knowledgeable of all relevant document updates concerning the clinical study (e.g Clinical study plan). Ensure that amendments to the protocol are provided to the MEC/IRB by the principal investigator.
- Ensure device accountability and check unapproved use outside the study.
- No structural source data verification is anticipated.

Names of the monitor(s) can be found in *Appendix 10: List of monitor(s)/Clinical Scientist(s)* of this protocol. An update of this list can be provided to the site under separate cover.

## 5. STATISTICAL CONSIDERATIONS

Any deviation from the planned analysis described below will be documented with justification in the final clinical end report.

### 5.1. Primary objective

#### Objective

To collect data on the amount of contrast used during PCI with the aid of Dynamic Coronary Roadmap to define a possible contrast reduction.

#### Endpoint

The primary endpoint of the study is the amount of contrast used during the PCI procedure. This will be defined as amount of iodine contrast in ml.

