### 1.2.1. Product Description Dynamic Coronary Roadmap [1]

Dynamic Coronary Roadmap is a software medical device intended to provide a real-time and dynamic angiographic roadmap of coronary arteries.

The angiographic roadmap is automatically generated from previously acquired diagnostic coronary angiograms during the same procedure.

Dynamic Coronary Roadmap overlays the angiographic roadmap on live 2D fluoroscopic images, thereby assisting the physician in navigating devices, e.g. (guide) wires, catheters, through the coronary arteries.

*Dynamic Coronary Roadmap is to be used in combination with a Philips interventional X-ray system.*

*When also used in conjunction with a compatible intravascular blood pressure measurement system, Dynamic Coronary Roadmap offers an FFR/iFR Roadmap feature which combines the information of the blood pressure within a coronary artery with an X-ray image of the pressure wire within that coronary artery, acquired when the pressure measurement was performed.*

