#### 4.3.3. Enrollment

Subjects are considered to be enrolled in the study after they have signed the informed consent form. No study procedures will be performed before this moment.

Subjects are enrolled in the study for the duration of the interventional procedure. No follow-up is required per protocol. Patient will be followed according to regular clinical standard of care.

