### 4.4. Procedures

Patients will receive standard medical treatment for their cardiac condition. During routine procedures, the physician may take angiograms for diagnosis which also serve as reference for device navigation. These angiograms will be automatically processed in the Dynamic Coronary Roadmap software and displayed as an overlay on the fluoroscopy for navigation support. In case a balloon catheter is used, the physician may take cine images when deflating the balloon as part of the standard care. These images can automatically be enhanced with the software and displayed. There is no follow up required after the procedure.

Phase 1: This is the phase where the physicians and study personnel can get used to the device and its capabilities. This phase serves to gain experience with the device and define workflow changes for the second phase. The use of Dynamic Coronary Roadmap makes these workflow changes possible and necessary in order to reduce the amount of contrast volume. It is estimated that 20 patients are necessary to gain enough experience and assess the workflow improvements.

Phase 2: This phase will focus on the contrast volume reduction. The defined workflow changes from phase 1 will be implemented in order to reduce the use of contrast volume. The minimal amount of contrast and timing of dosing will be defined. All other doses need to be avoided, as long as clinically acceptable. It is estimated that 25 patients are necessary to gain enough data to support the primary endpoint. This dataset will be compared with retrospective data from 25 patients that were treated without Dynamic Coronary Roadmap, preferably in the same timeframe.

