#### Endpoint

The endpoint is procedural timing. This is defined as the time from start of the procedure (catheter inserted) until end of the procedure (catheter removed) and time until first stent is placed.

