#### Endpoint

The endpoint is procedural information. This is defined as information on treated vessels, number of lesions, number of stents, type of lesion, catheter access site, lesion complexity, IVUS usage, OCT usage and FFR usage. These endpoints are typically recorded for patients undergoing coronary interventions, also for non-study patients.

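### The contrast endpoint does not say that same-session diagnostic and roadmap angiograms count, and planned versus ad hoc PCI is not listed for balancing the two groups

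*Protocol*

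**What the plan says.** Section 5.1 gives the primary endpoint in two sentences: "The primary endpoint of the study is the amount of contrast used during the PCI procedure", and "This will be defined as amount of iodine contrast in ml". It sets no start or stop point for counting and does not mention diagnostic injections.

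Elsewhere the protocol places diagnostic imaging inside the same session. Section 4.4 says that "the physician may take angiograms for diagnosis which also serve as reference for device navigation", and section 1.2.1 says that the roadmap is "automatically generated from previously acquired diagnostic coronary angiograms during the same procedure". Section 5.2.3 bounds the procedure by catheter insertion and catheter removal, but only for the timing endpoint.

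The inclusion criteria admit any PCI. The exclusion criteria remove emergency treatment and primary angioplasty for acute ST-elevation infarction. Planned and ad hoc PCI are both otherwise eligible.

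Section 4.4 compares 25 Phase 2 subjects with 25 retrospective patients treated without the roadmap. The study is not randomized, and no selection of controls by type of PCI is stated. The only test named in 5.1 is an optional t-test. The procedural items in 5.2.4 are "treated vessels, number of lesions, number of stents, type of lesion, catheter access site, lesion complexity, IVUS usage, OCT usage and FFR usage".

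**The concern.** In this trial a single injection can be both diagnostic and part of the device workflow, so the boundary of PCI contrast needs to be written down. It also needs to be the same for prospective subjects and for whoever extracts the retrospective records.

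Settling the boundary as the whole session exposes a second issue. A patient whose diagnostic study and PCI take place in one sitting will tend to receive more contrast than a patient who returns for a planned PCI on known anatomy, with or without the device. If the share of such patients differs between the groups, that difference goes straight into the estimated contrast reduction. The item that would reveal it is not on the protocol's list.

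The estimate has a use beyond description. Section 4.1 says that the pilot is to power a pivotal study, and section 3.1 links the programme to a possible contrast reduction claim.

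**Working it through.** **Step 1. The plan's own figure.** The protocol gives no alpha, power, effect size or SD, so there is no power calculation to reproduce. The total is consistent: 20 (Phase 1) + 25 (Phase 2) = 45. Nothing below depends on it.

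**Step 2. Which counting window does the text imply?**
- Section 1.2.1: the diagnostic angiograms that build the roadmap belong to the same procedure.
- Section 5.2.1: the radiation endpoint uses the same phrase about the PCI procedure and reports total DAP and total AK.
- Section 5.2.3: the procedure runs from catheter in to catheter out.

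Together these point to all contrast in the session, roadmap angiograms included. Section 5.1 does not say so and does not refer to 5.2.3.

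**Step 3. Effect of an imbalance under that window, with a device that does nothing.**

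Shift in (control mean - Phase 2 mean) = D x (p_C - p_T)

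D is the extra contrast from a same-session diagnostic study. p_C and p_T are the ad hoc shares in controls and in Phase 2. None of these is in the protocol. D = 40 to 80 ml and p_C - p_T = -40 to +40 points are assumptions, and D is taken as equal in both groups.

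| D (ml) | -40 pts | -20 pts | 0 | +20 pts | +40 pts |
|---|---|---|---|---|---|
| 40 | -16 | -8 | 0 | +8 | +16 |
| 60 | -24 | -12 | 0 | +12 | +24 |
| 80 | -32 | -16 | 0 | +16 | +32 |

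A positive entry looks like a contrast reduction. A negative entry hides a real reduction or looks like an increase.

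**Step 4. What the optional t-test would do with such a shift.** Two-sided 5% test, 25 versus 25, 48 degrees of freedom, noncentrality = shift / (SD x sqrt(2/25)). The SD is assumed to be 50, 70 or 90 ml. Example: 32 / (50 x 0.283) = 2.26. The results are the same for either sign.

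| Shift (ml) | SD 50 | SD 70 | SD 90 |
|---|---|---|---|
| 0 | 5% | 5% | 5% |
| 16 | 20% | 12% | 9% |
| 32 | 60% | 35% | 23% |

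**Step 5. Could an imbalance arise without any selection?** If both groups have the same true ad hoc share, the chance of an observed difference of at least 20 points (5 patients or more out of 25), in either direction, follows from two independent binomials. It is 16% for a share of 30%, 20% for 50% and 16% for 70%. Recording the item is therefore worthwhile even if no systematic selection operates.

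**The case against.** The strongest reply is that the window is less open than it looks. Sections 1.2.1, 5.2.1 and 5.2.3 read naturally as the whole session, and nothing sets different windows for the two groups. This stands: taken alone, the window needs only a clarifying sentence. The reply does not remove the case-mix issue, because the whole-session reading is the one that loads diagnostic contrast onto ad hoc cases.

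A second reply is that this is a descriptive, openly non-randomized pilot without pass or fail criteria, and that adjustment is commonly left to an analysis plan, which is not shown here. This limits the harm to a biased estimate rather than a wrong decision rule. However, an analysis plan can adjust only for an item collected in both groups.

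A reader might also infer more than the documents support:
- **That the bias favours the device.** Section 4.3.3 says "Subjects are considered to be enrolled in the study after they have signed the informed consent form", which might suggest that Phase 2 leans toward planned cases. But a patient can consent before a catheterization that may proceed to PCI, and section 4.4 expects diagnostic angiograms in device cases. The direction is not documented.
- **That planned or ad hoc status is not recorded.** Section 6 says that the e-CRF captures procedure-related information, and its fields are not shown. The documents support only the statement that it is not listed in 5.2.4.
- **That diagnostic contrast would be subtracted, removing the roadmap injection from the device total.** No section proposes this.

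**Conclusion.** The point holds in a limited form. The protocol does not state that same-session diagnostic and roadmap angiograms count toward the primary endpoint, or that one counting rule covers both groups. The whole-session meaning is nevertheless the natural one. Under it, a difference between the groups in same-session diagnostic angiography enters the contrast difference directly. The protocol does not list planned versus ad hoc status and neither selects nor adjusts for it.

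The bias can go either way and is zero if the groups are balanced. On the assumed inputs it reaches 32 ml in either direction. That figure shows what an imbalance could do and is not an estimate for this trial. What is at stake is the contrast difference carried into the pivotal design.

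**What to change.** - **Section 5.1:** state that all contrast injected from catheter insertion to catheter removal counts, including the angiograms used to build the roadmap, and that the same rule applies to Phase 2 subjects and to the retrospective records.
- **Section 5.2.4:** add planned or ad hoc PCI (same-session diagnostic angiography, yes or no), collected for Phase 2 subjects and for controls.
- **Comparison:** select the 25 controls by this item, or report the contrast difference stratified by it or adjusted for it. This step is essential, because the whole-session window on its own leaves the diagnostic contrast of ad hoc cases in the comparison.

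The cost is two short text changes and one extra chart or e-CRF field. Stratifying 25 versus 25 gives up a little precision. No additional patients or procedures are needed.

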#### Experimental design

The objective is descriptive with no performance requirements and no pass or fail criteria. All Phase 2 subjects will be included in this analysis.

#### Presentation format

Results will be described in summary statistics with median, confidence interval and standard deviation. Depending on the amount of data gathered during the clinical study a student t-test can be performed.

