## 4. STUDY DESIGN

### 4.1. General

This is a prospective, non-randomized, unblinded, observational, single-center study.

A non-randomized study design has been chosen to get first insights in contrast reduction with the use of Dynamic Coronary Roadmap. This study will serve as a pilot study to power a pivotal study at a later stage.

The results of the study population will be compared with retrospective data generated before the Dynamic Coronary Roadmap was installed.

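### The required comparison with 25 non-randomised retrospective patients rests on an optional Student t-test with an undefined trigger and no mention of case-mix adjustment (minor)

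*Protocol*

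**What the plan says.** The comparison is firm. Section 4.1 says: "The results of the study population will be compared with retrospective data generated before the Dynamic Coronary Roadmap was installed." Section 4.4 gives the comparator for Phase 2: "This dataset will be compared with retrospective data from 25 patients that were treated without Dynamic Coronary Roadmap, preferably in the same timeframe." The Summary repeats both statements. The design is non-randomised and unblinded.

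Section 5 presents itself as the plan of analysis: "Any deviation from the planned analysis described below will be documented with justification in the final clinical end report." For the primary endpoint, contrast volume in ml, section 5.1 promises: "Results will be described in summary statistics with median, confidence interval and standard deviation." It then adds the only comparative method: "Depending on the amount of data gathered during the clinical study a student t-test can be performed." It also sets the status of the result: "The objective is descriptive with no performance requirements and no pass or fail criteria."

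Two further statements bear on how the result will be read. Its later use is given in section 4.1: "This study will serve as a pilot study to power a pivotal study at a later stage." Phase 2 also changes more than the software, as section 4.4 states: "The defined workflow changes from phase 1 will be implemented in order to reduce the use of contrast volume."

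Section 5.2.4 collects number of lesions, lesion complexity and other procedural items in order to describe the study population. It notes that these are usually recorded for patients outside the study as well. It does not link them to the contrast comparison.

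**The concern.** The plan makes the comparison compulsory and the method for it discretionary. The condition on the t-test depends on how much data is gathered, with no number attached, yet 25 against 25 is already planned. Running the test and omitting it would both comply, so the rule that deviations must be justified does not constrain the choice.

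The named method also suits the design poorly. Nothing in a non-randomised comparison balances the number or difficulty of lesions between the groups. If these differ and are related to contrast use, an unadjusted mean difference mixes that effect with the effect of device and workflow, in either direction, and its CI does not reflect the mixture. What is at stake is the planning estimate carried forward to a pivotal study. No decision within this study depends on it.

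**Working it through.** **The plan's own figure.** Phase 1 has 20 patients and Phase 2 has 25: 20 + 25 = 45, which agrees with the stated total. The protocol gives no SD, effect size, power or alpha, so nothing further can be reproduced. Results below are in units of the within-group SD of contrast volume.

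**Inputs from the protocol.** Phase 2 n = 25 and retrospective n = 25 (section 4.4); a continuous endpoint (section 5.1).

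**Assumed inputs.** A two-sided 95% CI and a common SD; case mix explains a share R² of within-group variance, from 0.1 to 0.5; the groups differ on the case-mix score by D, from 0.3 to 0.5 SD. The documents give none of these.

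**Step 1: is a data-volume trigger needed?** The CI half-width for a difference in means is t(2n−2, 0.975) × √(2/n).

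| n per group | t | √(2/n) | Half-width (SD) |
|---|---|---|---|
| 25 | 2.011 | 0.283 | 0.569 |
| 20 | 2.024 | 0.316 | 0.640 |
| 15 | 2.048 | 0.365 | 0.748 |

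The difference can be reported with its CI at any of these sizes. Fewer patients widen the interval but give no reason to withhold it.

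**Step 2: shift and coverage of the unadjusted difference.** The shift is √R² × D. Coverage comes from the noncentral t with 48 df and noncentrality shift × √(25/2) = shift × 3.536.

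| R² | D | Shift (SD) | Noncentrality | Coverage of the 95% CI |
|---|---|---|---|---|
| 0.1 | 0.3 | 0.095 | 0.335 | 0.94 |
| 0.3 | 0.5 | 0.274 | 0.968 | 0.84 |
| 0.5 | 0.5 | 0.354 | 1.250 | 0.77 |

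As a share of the half-width, the shift runs from 0.095/0.569 = 17% to 0.354/0.569 = 62%.

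**Step 3: what adjustment does.** In a simulation with 10,000 runs per setting, 25 v 25, the regression adjusts for the case-mix score and one irrelevant covariate.

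| R², D | Coverage, unadjusted | Coverage, adjusted | Root mean square error, unadjusted | Root mean square error, adjusted |
|---|---|---|---|---|
| 0.1, 0.3 | 0.941 | 0.956 | 0.295 | 0.272 |
| 0.3, 0.5 | 0.839 | 0.951 | 0.396 | 0.250 |
| 0.5, 0.5 | 0.771 | 0.952 | 0.451 | 0.211 |

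This is a best case, because the covariate captures the whole imbalance. If it captures part, only that part is removed. With weak covariates there is little or no gain in precision: the adjusted and unadjusted half-widths are 0.567 and 0.566 SD at R² = 0.1, D = 0.5, and 0.598 and 0.566 SD at R² = 0, D = 0.5, about 6% wider.

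**The case against.** The strongest reply is that most of this is detail for a statistical analysis plan. The sentence sits under a heading about presentation, nothing in section 5 forbids adjustment, and a CI is already promised. That stands for the quantity the CI refers to and for the absent mean, which are reporting detail and are not pressed here. It does not dispose of the t-test sentence. There the protocol states a method for a comparison it requires, and ties it to a condition that it does not define.

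A second reply is that the study is a descriptive pilot without pass or fail criteria. That also stands and limits the weight. A reader might infer an inflated false-positive rate, but the protocol sets no test on which anything depends. A reader might also infer that the groups are in fact unbalanced, and no data in the documents show this.

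A reader might go further and infer that confounding would mis-size the pivotal trial by a calculable amount. The documents do not support that. They do not say that the pivotal study will be sized on the raw point estimate, and sampling error alone produces a similar spread. Take an assumed true difference of 0.6 SD and a standard error of √(2/25) = 0.283 SD. The 10th to 90th percentile of the pilot estimate is 0.6 ± 1.28 × 0.283, or 0.24 to 0.96 SD. The largest shift in the working gives 0.6 ± 0.354, or 0.25 to 0.95 SD. Adjustment addresses the shift and leaves the sampling error.

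Finally, adjustment cannot repair differences in calendar time or in how the controls were chosen, which may matter more. That is correct, and the revised wording should say so.

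**Conclusion.** The point holds as a minor one. A compulsory, non-randomised comparison is paired with an optional test whose trigger is undefined and unnecessary at the planned sizes, and no use is made of case-mix items that the study already collects. On the assumed inputs, the unadjusted estimate could be off by about 0.09 to 0.35 SD, with CI coverage between 94% and 77%. Coverage returns to about 95% if the covariates capture the imbalance. These figures illustrate a range and predict nothing about this centre's patients. They rest on the assumed R² and imbalance, and on equal SDs.

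**What to change.** Replace the t-test sentence in section 5.1 with:

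*The Phase 2 v retrospective difference in contrast volume will be reported with its 95% CI, unadjusted and, as a supporting analysis, adjusted by linear regression for a small set of case-mix items from 5.2.4 (for example number of lesions and lesion complexity), chosen and defined identically in both groups before contrast volumes are compared.*

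Add that the estimate reflects device and workflow change together, and that adjustment does not remove calendar-time or control-selection differences.

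The cost is protocol wording, a few degrees of freedom, a written definition of lesion complexity (section 5.2.4 gives none) and extraction of the chosen items from 25 control records. If the covariates are only weakly prognostic, there is little or no gain in precision and the CI may widen slightly. If they are missing in the controls, only the unadjusted difference remains, but it would still be reported with its CI.
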